5.3 Grooved Pegboard Test (GPT)

The Grooved Pegboard Test is a manual dexterity test measuring visual-motor coordination (Lafayette 2002). The test consists of a pegboard with 25 holes with randomly positioned slots and pegs with a key along one side. The subject is to insert the pegs as quickly as possible into the slots in sequence, first with the dominant hand and then with the non-dominant hand. The score is the time it takes for the subject to complete the task with each hand. For subjects who fail to complete the test in 5 minutes the score is the number of total pegs inserted. In addition, to time to completion, the number of pegs dropped (for each hand) is recorded.

Changes from baseline for these GPT scores will be summarized for each hand (dominant and non-dominant) at each scheduled timepoint (Days 6, 28, 85, 90, 112, and 168) (Table 14.2.3).

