1 INTRODUCTION

This statistical analysis plan (SAP) describes the planned statistical analyses for the study entitled “A Prospective, Randomized, Double-Blind, Dose-Comparison Concurrent Control Study to Assess the Safety and Tolerability of GRF6019 Infusions in Subjects with Mild to Moderate Alzheimer’s Disease” (V6.0 12OCT2018, V7.0 02NOV2018). Analysis related to exploratory objectives (assessment of changes in composition and distribution of blood-based and CSF (in consenting subjects) biomarkers, as well as changes in imaging results as measured by vMRI, fMRI, and ASL) will be described in a separate plan. Mock shells for the CSR Appendix 14 are also produced as a separate working document to facilitate programming of Tables, Figures, and Listings (TFLs) according to the finalized SAP. The SAP is to be interpreted in conjunction with the protocol. If the final clinical study report contains changes to any planned statistical analyses, the justification for any such differences will be fully documented in the CSR.

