2 GENERAL ANALYSIS DEFINITIONS

All analysis dataset preparations and statistical analyses will be performed using SAS® version 9.4 or higher. No imputation will be performed for missing data unless stated otherwise. Listings for CSR Appendix 16.2 will include all the subject data points being collected or derived for analyses, and will be sorted by treatment group, site, and subject number.

[figure not shown]

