2.6 Descriptive Summaries

All tabulated summaries will include the two treatment groups [REDACTED] and overall (includes data from both treatment groups). For endpoints that are continuous in nature: number of observations, mean, median, minimum and maximum, and standard deviation (SD) values will be presented as descriptive summary. For endpoints that are categorical in nature: frequency counts and percentages will be presented in the descriptive summary.

The number of decimal places to display for calculated data will be determined by the original scale of the data. Means, medians, and confidence intervals will be reported with one (1) additional decimal place. Standard deviation will be reported with two (2) additional decimal places. Minimum and maximum will be reported with the same number of significant digits as the method of capture.

For all efficacy and safety tables summarizing change from baseline, the baseline and post-baseline results at all planned timepoints will be included.

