Table 14.1.4.2	Baseline Assessment of Columbia-Suicide Severity Rating Scale (C-SSRS)	SAF
Table 14.1.4.3	APOE Genotype	SAF
Table 14.1.5.1	Medical History	SAF
Table 14.1.5.2	Social History	SAF
Table 14.1.5.4	Exercise-Activity Level	SAF
Table 14.1.5.5	Tobacco Use	SAF
Table 14.1.5.6	Alcohol and Illicit Substance Use	SAF
Table 14.1.6.1	Prior Medication	SAF
Table 14.1.6.2	Concomitant Medication	SAF
Table 14.1.7.1	Exposure to Study Drug	SAF
Table 14.1.7.2	Actual infusion rate at each time point per infusion day	SAF
Table 14.1.7.3	Numbers of below, within and above the designated infusion rate reference	SAF
Table 14.1.7.4	Overall infusion parameters per infusion day	SAF
Table 14.1.8.1	Completion of Study Drug	SAF
Table 14.1.8.2	Number of subjects completing 5 and 10 infusions	SAF
Table 14.1.9.1	Number of subjects completing 8 weeks after receiving at least 5 infusions	SAF
Table 14.1.9.2	Number of subjects completing 24 weeks after receiving at least 10 infusions	SAF
Table 14.1.10.1	Visit Compliance	SAF
Figure 14.1.10.2	Kaplan-Meier curves of the time to completion or discontinuation of the trial	SAF
Table 14.2.1	Changes in scores on the Mini-Mental State Examination (MMSE)	EVAL, PPROT
Table 14.2.2	Changes in scores on the 11-item Alzheimer's Disease Assessment Scale-Cognitive Subscale (ADAS-Cog/11)	EVAL, PPROT
Table 14.2.3	Changes in scores on the Grooved Pegboard Test	EVAL, PPROT
Table 14.2.4	Changes in scores on the Category Fluency Test	EVAL,

Number	Title	Population
	(CFT)	PPROT
Table 14.2.5	Changes in the Clinical Dementia Rating Scale – Sum of Boxes (CDR-SOB)	EVAL, PPROT
Table 14.2.6.1	Changes in the Alzheimer’s Disease Cooperative Study – Activities of Daily Living23 (ADCS-ADL23) for Subjects	EVAL, PPROT
Table 14.2.6.2	Changes in the Alzheimer’s Disease Cooperative Study – Activities of Daily Living23 (ADCS-ADL23) for Partners	EVAL, PPROT
Table 14.2.7	Changes on the Alzheimer’s Disease Cooperative Study – Clinical Global Impression of Change (ADCS-CGIC)	EVAL, PPROT
Table 14.2.8	Change on the Neuropsychiatric Inventory Questionnaire (NPI-Q)	EVAL, PPROT
Table 14.3.1.1.1	Overall Summary of Treatment-Emergent Adverse Events (TEAE)	SAF
Table 14.3.1.1.2	Overall Summary of Treatment-Emergent Adverse Events (TEAE) in Period 1	SAF
Table 14.3.1.1.3	Overall Summary of Treatment-Emergent Adverse Events (TEAE) in Period 2	SAF
Table 14.3.1.2.1.1	Incidence of Treatment-Emergent Adverse Events (TEAEs) by MedDRA System Organ Class and Preferred Term	SAF

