11 LISTINGS FOR CSR APPENDIX 16.2

Number	Title	Population
Listing 16.2.1.1	Analysis Populations	SCRN
Listing 16.2.1.2	Screen Failures	SCRF
Listing 16.2.1.3	Subject Disposition	ITT
Listing 16.2.1.4	Protocol Deviations	ITT
Listing 16.2.1.5	Informed Consent	ITT
Listing 16.2.1.6	Study Visits	ITT
Listing 16.2.2.1	Inclusion Criterion Not Met or Exclusion Criteria Met	ITT
Listing 16.2.2.2	Assessment for AD using NIA-AA criteria	ITT
Listing 16.2.2.3	Drug Testing/Serology Screen	ITT
Listing 16.2.2.4	Randomization	ITT
Listing 16.2.3.1	Demographics	ITT
Listing 16.2.3.2	Baseline Characteristics	ITT
Listing 16.2.3.3	Baseline Assessment of Modified Hachinski Ischemia Scale (MHIS)	ITT
Listing 16.2.3.4.1	Columbia-Suicide Severity Rating Scale (C-SSRS) Lifetime	ITT
Listing 16.2.3.4.2	Columbia-Suicide Severity Rating Scale (C-SSRS) Last 6 Months	ITT
Listing 16.2.3.5	APOE Genotype	ITT
Listing 16.2.4.1.1	Medical History	SAF
Listing 16.2.4.1.2	Alzheimer's Disease History	SAF
Listing 16.2.4.2	Family Medical History	SAF
Listing 16.2.4.3	Social History	SAF
Listing 16.2.4.4	Exercise/Activity Level	SAF
Listing 16.2.4.5	Tobacco Use	SAF
Listing 16.2.4.6	Alcohol and Illicit Substance Use	SAF
Listing 16.2.4.7	PET Scan	SAF
Listing 16.2.4.8	Echocardiogram Results	SAF
Listing 16.2.5.1.1	Prior Medications	SAF
Listing 16.2.5.1.2	Previous Treatment for Alzheimer's Disease	SAF
Listing 16.2.5.2	Concomitant Medications	SAF
Listing 16.2.5.3	Extent of Exposure	SAF
Listing 16.2.5.4	Infusion Rate	SAF
Listing 16.2.5.5	Daily Summary of Infusion Administration	SAF
Listing 16.2.5.6	Treatment Completion	SAF
Listing 16.2.5.7	Tolerability	SAF
Listing 16.2.5.8	Assessment of Blinding	SAF
Listing 16.2.6.1	Mini-Mental State Examination (MMSE)	ITT
Listing 16.2.6.2	Alzheimer's Disease Assessment Scale-Cognitive Subscale (ADAS Cog/11)	ITT

Number	Title	Population
Listing 16.2.6.3	Grooved Pegboard Test (GPT)	ITT
Listing 16.2.6.4	Category Fluency Test (CFT)	ITT
Listing 16.2.6.5	Clinical Dementia Rating Scale – Sum of Boxes (CDR-SOB)	ITT
Listing 16.2.6.6	Alzheimer’s Disease Cooperative Study – Activities of Daily Living 23 (ADCS-ADL23)	ITT
Listing 16.2.6.7	Alzheimer’s Disease Cooperative Study – Clinical Global Impression of Change rating (ADCS-CGIC)	ITT
Listing 16.2.6.8	Neuropsychiatric Inventory Questionnaire (NPI-Q)	ITT
Listing 16.2.7.1	Non Treatment Emergent Adverse Events	SAF
Listing 16.2.7.2	Treatment Emergent Adverse Events	SAF
Listing 16.2.8.1	Clinical Laboratory Results	SAF

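### SAP 5.3 scores the Grooved Pegboard in seconds for finishers and in pegs for non-finishers, with no rule for change from baseline when a subject crosses the 5-minute limit

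*SAP*

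**What the plan says.** SAP 5.3 gives two definitions in successive sentences. For a subject who finishes, "The score is the time it takes for the subject to complete the task with each hand". For one who does not, "For subjects who fail to complete the test in 5 minutes the score is the number of total pegs inserted". It also records pegs dropped, per hand. The analysis is then: "Changes from baseline for these GPT scores will be summarized for each hand (dominant and non-dominant"), at each scheduled timepoint, in Table 14.2.3.

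Other parts of the plan that bear on this:

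- SAP 2: "No imputation will be performed for missing data unless stated otherwise".
- SAP 2.6: for continuous endpoints, "number of observations, mean, median, minimum and maximum, and standard deviation (SD) values will be presented as descriptive summary". Its last sentence has change-from-baseline tables also show the baseline and post-baseline results at every planned timepoint.
- SAP 5: a paired t-test, and ANCOVA with baseline and sex, may be run for the efficacy endpoints.
- SAP 1: "Mock shells for the CSR Appendix 14 are also produced as a separate working document". The shells are not among the documents reviewed.
- Protocol 7.1.1.3.3 defines the score as time only, with no time limit and no peg count. SAP 8 does not list the 5-minute rule as a change.
- Protocol 10.4.1 allows rank-ANCOVA or other non-parametric methods if Normality fails.

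**The concern.** The two quantities differ in unit and direction. The SAP states no direction, but the task is timed and done at speed, so more seconds is worse and more pegs is better. Among 25 holes a non-completer scores 0 to 24. A subject who finishes at one visit and not at the other has one value of each kind, and no section says what the change is. The SAP writes such rules where it sees the need: SAP 5.1 says what to do with one missing MMSE item and with more than one. SAP 5.3 has no equivalent.

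At stake is whether the time-change summary, and any test of it, represents all subjects tested or only those who finished at both visits. Being left out depends on the outcome itself, so it is not ordinary missing data.

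**Working it through.** The plan gives no figure to reproduce here. It also gives no completion times, SDs or non-completion rates, so everything beyond step 2 rests on assumption.

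**1. One subject who worsens across the limit.** Assume 280 s at baseline and 22 pegs at follow-up.

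- Literal reading: 22 - 280 = -258, which looks like a large improvement.
- Time scale: the follow-up time exceeds 300 s, so the change is at least 300 - 280 = +20 s.
- Separate parameters: no time at follow-up and no peg count at baseline, so no change on either.

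**2. Effect of that subject on an arm mean.** About 30 evaluable subjects (SAP 1.3) is about 15 per arm; 20 per arm are randomized. Assume all other subjects change by +10 s.

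| | n = 15 | n = 20 |
|---|---|---|
| 300 s cap | (14×10 + 20)/15 = +10.7 | (19×10 + 20)/20 = +10.5 |
| Separate rows (subject absent) | 140/14 = +10.0 | 190/19 = +10.0 |
| Literal | (140 - 258)/15 = -7.9 | (190 - 258)/20 = -3.4 |

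Literal minus cap is (-258 - 20)/n = -278/n: -18.5 at n = 15 and -13.9 at n = 20. Separate rows move the mean little; the literal reading reverses its sign.

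**3. How often, under assumed inputs.** Simulated subjects had baseline mean (SD) 150 (50), 180 (60) or 220 (60) s and a true slowing of 10, 20 or 30 s. Times were kept at 60 s or above. A 35 s SD was placed either on the change (model A) or independently on each visit (model B). That makes 3 × 3 × 2 = 18 scenarios.

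- Subjects crossing the limit in either direction: 1.1% to 17.4%, or about 0.2 to 2.6 per 15.
- Chance of at least one crosser per arm, for one hand at one visit, 1 - (1 - p)^n with p from 1.07% to 17.35%: 15% to 94% at n = 15, and 19% to 98% at n = 20.
- Share of crossers who worsened: 83% to 99% (model A), 63% to 85% (model B).
- Mean change, separate rows minus 300 s cap: largest absolute gap 1.03 s (model A) and 1.24 s (model B).

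Two limits apply. The 35 s SD was not varied; a larger SD produces more crossers and can widen the gap, so about 1 s describes these inputs and is not a bound. The worsening share also depends on the assumed slowing: with none, model B would split crossers evenly.

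**4. Whether planned output reveals the crossers.** With separate rows and the SAP 2.6 layout, n on the pegs-inserted row at a visit is the number of non-completers. At a visit, n(pegs) minus n(change in pegs) counts those who crossed by worsening, and n(time) minus n(change in time) counts those who crossed by improving, apart from subjects with no baseline test. Listing 16.2.6.3 shows each subject. The numbers can be derived, but no row names them.

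**The case against.** The strongest reply is that nobody would subtract seconds from pegs. SAP 5.3 names several quantities and then speaks of scores in the plural. Putting several scores in one table is this SAP's usual layout: ADAS-Cog total and domains in Table 14.2.2, CDR global and SOB in 14.2.5, NPI-Q severity and distress in 14.2.8. The mock shells may settle the rows. This stands. A reader might infer from the two definitions that Table 14.2.3 will mix units; the documents leave that possible but do not show it is intended.

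A reader might also infer that crossers vanish without trace. That is not supported either: their number and direction follow from the planned n's and the listing, as in step 4. What is missing is a label.

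Third, the tests are optional, p values are nominal, and Protocol 10.4.1 already permits rank methods. That is true, but a rank analysis of change in time still has no value for a crosser unless the plan says where non-completers rank, and Protocol 10.4.1 does not.

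The gap that remains holds on either reading: no rule gives a subject who crosses the limit a usable change score.

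**Conclusion.** The point holds and is minor. SAP 5.3 defines a score whose type can differ between visits and plans change from baseline without a rule for that case. On the natural reading, the time-change summary and any test of it exclude subjects because of performance, and mostly those who worsened if the group is slowing. On the literal reading, individual changes have the wrong sign.

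The effect on the mean with separate rows is small under the assumed inputs, about 1 s against a 300 s cap, with the SD caveat above. A reader might infer that the trial's conclusions are at risk. They are not: the test is one of nine secondary cognitive and functional measures in Protocol 4.2.2, which says the study is not powered for cognitive or motor differences, and the primary endpoints do not use it. The argument for acting is that the fix is nearly free and uses data already collected, and that a rule fixed before lock and unblinding avoids a choice made with the results in view.

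**What to change.** In SAP 5.3, before database lock:

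(a) State that time, pegs inserted and pegs dropped are separate parameters for each hand, and that time is never differenced against pegs.

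(b) Add labelled rows for the number (%) not completing in 5 minutes and the number with no change score because they crossed the limit, by hand, visit and group, at the visits where the test is given.

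(c) For any test of change in time, pre-specify one rule that keeps non-completers in. Preferred: a rank analysis placing every non-completer below all completers, ordered by pegs inserted, for instance rank-ANCOVA with baseline rank and sex as covariates. Acceptable: set non-completers to 300 s, stating that this understates decline beyond 300 s.

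Listing the 5-minute rule in SAP 8 would be optional housekeeping.

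Cost: a few lines of wording, the count rows and one derivation, with no new data. Items (a) and (b) have no statistical downside. Under (c), the rank result is not in seconds, and the cap replaces unknown times with one fixed value.

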5.4 Category Fluency Test (CFT)

Category fluency tasks are an important component of neuropsychological assessment, especially when evaluating for dementia syndromes. Subjects are asked to generate words from a specified semantic category (e.g., name as many different types of animals, vegetables, or fruits in a 60 second period) (Acevedo 2000). The number of correct, non-repeated responses constitutes the primary CFT raw score. In addition, the number of repetitions and other errors is recorded.

Changes from baseline for CFT scores will be summarized for each scheduled timepoint (Days 28, 112, and 168) (Table 14.2.4).

5.5 Clinical Dementia Rating Scale – Sum of Boxes (CDR-SOB)

The Clinical Dementia Rating Scale (CDR) is a global assessment instrument that yields Global and Sum of Boxes (SOB) scores, with the global score regularly used in clinical and research settings to stage dementia severity. The CDR is obtained via semi-structured interviews with patients and informants (e.g. trial partners) to characterize functioning in 6 domains: memory, orientation, judgment and problem solving, community affairs, home and hobbies and personal care (Hughes 1982). Each domain is rated on a 5-point scale, and the CDR-SOB score is obtained by summing each of the domain box scores. The CDR-SOB is considered a more detailed quantitative general index than the Global score (O'Bryant 2008).

Changes from baseline for CDR global and CDR-SOB scores will be summarized at each scheduled timepoint (Days 28, 112, and 168) (Table 14.2.5).

5.6 Alzheimer's Disease Cooperative Study – Activities of Daily Living 23 (ADCS-ADL23)

The ADCS-ADL is an inventory of informant-based items used to assess activities of daily living and instrumental activities of daily living, (i.e., functional performance) for AD subjects (Galasko 1997). The interviewer asks the subject's caregiver a total of 23 questions regarding the subject's ability to maintain good hygiene, use a telephone, initiate conversations, etc. A score of up to 4 points may be assigned to each question. A higher score indicates less impairment; the maximum achievable score (indicating no ADL impairment) is 78. The sum of the responses for the 23 items of the inventory will be calculated for the total score and recorded into eCRF.

Changes from baseline for ADCS-ADL23 total score will be summarized for subject and trial partner separately, and at each scheduled timepoint (Days 28, 56, 112, 140, and 168) (Table 14.2.6.1 and 14.2.6.2).

5.7 Alzheimer's Disease Cooperative Study – Clinical Global Impression of Change rating (ADCS-CGIC)

The ADCS-CGIC is a process for obtaining an assessment of meaningful clinical change over time (Schneider 1997). It is a systematic method for assessing clinically significant change in a clinical trial as viewed by an independent skilled and experienced clinician. The ADCS-CGIC focuses on clinicians' observations of change in the subject's cognitive, functional and behavioral performance since the beginning of a trial. It relies on both direct examination of the subject and interview of informants. Unlike a targeted symptom scale, it takes into account a subject's overall functioning in the cognitive, behavioral and functional activity domains.

The ADCS-CGIC is a single value score based on a 7-point scale using the following values:

- 1 = Marked Improvement
- 2 = Moderate Improvement
- 3 = Minimal Improvement
- 4 = No Change
- 5 = Minimal Worsening
- 6 = Moderate Worsening
- 7 = Marked Worsening

Changes from baseline for ADCS-CGIC rating (1-7) will be summarized at each scheduled timepoint (Days 28, 112, and 168) (Table 14.2.7).

5.8 Neuropsychiatric Inventory Questionnaire (NPI-Q)

The NPI-Q evaluates the most frequent neuropsychiatric manifestations of dementia and determines their frequency and intensity (Kaufers 2000). It is designed to be a self-administered questionnaire completed by informants (e.g. trial partners) about subjects for whom they care. Generally, the NPI-Q is used to evaluate changes in subject behavior that have appeared during a given period. The NPI-Q comprises 12 domains: delusions, hallucinations, dysphoria, apathy, euphoria, disinhibition, aggressivity and restlessness, irritability, anxiety, aberrant

motor behavior, appetite and eating disorders, and nocturnal behavior. Initial responses to each domain question are "Yes" (present) or "No" (absent). If the response to the domain question is "No", the informant goes to the next question. If "Yes", the informant then rates both the severity of the symptoms present within the last month on a 3-point scale and the associated impact of the symptom manifestations on them (i.e., trial partner distress) using a 5-point scale. Thus, the NPI-Q evaluates response to therapy and provides symptom severity and distress ratings for each symptom reported, and total severity and distress scores reflecting the sum of individual domain scores.

Change from baseline for NPI-Q total severity score and total distress score will be summarized at each scheduled timepoint (Days 28, 56, 112, 140, and 168) (Table 14.2.8).

6 SAFETY

All safety analyses will be done on the Safety Set.

6.1 Adverse Events

6.1.1 Coding of AEs

The verbatim terms of AEs will be coded using the Medical Dictionary for Regulatory Activities (MedDRA). Events are looked at on the level of their preferred term and system organ class.

6.1.2 Treatment-Emergent AE

Pre-treatment AEs are defined as AEs that were reported or worsened after signing the ICF up to the start of study drug dosing. Treatment-emergent AEs (TEAE) are defined as AEs that were reported or worsened on or after the start of study drug dosing and up to and including the end of the follow-up.

6.1.3 Period Allocation of AE

Adverse events are allocated to a period based on their start date and time. If the start date and time of an event falls between (or on) the start and stop date and time of a period, the AE is attributed to that period (treatment-emergent principle).

Rule: period start datetime \leq AE start datetime \leq period stop datetime.

In case of partial AE start dates and or times, the events are allocated to the periods using the available partial information on start and end datetime; no imputation will be done. If, for instance, for the AE start date only month and year are available, these data are compared to the month and year information of the periods. This rule may lead to multiplication of the event as a consequence of its assignment to multiple periods. In case of a completely missing AE start date, the event is allocated to the first period, except if the end date of the AE falls before the start of this period. In case of any other missing scenarios, the period allocation of AE will be determined by manual data review prior to database lock.

6.1.4 Variables Attributed to Adverse Events:

- AE term (verbatim and MedDRA preferred term and system organ class)
- Onset datetime, End datetime, and duration of AE
- Serious AE (Yes/No), if yes classification will be listed
- Severity (Mild, Moderate, Severe)
- Relation to study treatment (Unrelated, Possibly Related, Definitely Related)
- Frequency (Single Episode, Intermittent, Continuous)
- Action taken with study treatment (No Action Taken, Treatment Held, Treatment Discontinued)
- Other Action due to AE (Medication Therapy, Non-Drug Therapy, Other)
- Outcome of AE (Recovered/Resolved, Not Recovered/Not Resolved, Resolved/Resolved with Sequelae, Fatal, Unknown)
- AE leading to death (Yes/No)
-
- AE of special interest

